3rd December 2021

Study protocol with SAP

The supervised multimodal training in the present 19-weeks study was offered to postmenopausal healthy women in a local community. The outcomes for the training group (MMT) were compared with a sedentary control group (CON). Training was offered twice weekly for one hour, and the average attendance rate of MMT participants over the 19wk had to be > 1 hour weekly.

To collect baseline (BASE) data, all participants showed up in the laboratory at three occasions prior to the intervention. On the first visit, resting blood samples were collected to evaluate the concentration of bone turnover markers (BTM), and body weight, height, body composition, bone mineral density (BMD) and bone mass were measured. On the second visit, a dynamic balance test (four square step test) and a functional muscle strength and power test (jump-and-reach test) were performed. On the third visit, the aerobic capacity was evaluated by assessment of VO₂-max. After three weeks (3wk) of training, resting blood samples were collected again. After 19wk of training, all assessments were repeated and compared with baseline, and MMT and CON were finally compared.

[figure not shown]
Blood sample collection, DXA-scanning, and VO₂-max tests were carried out at the Department of Nutrition, Exercise and Sports, University of Copenhagen, Denmark. The training and testing of vertical jump height, as well as dynamic balance, were performed at the health promotion training initiative in the Copenhagen area, Denmark. The blood samples were analyzed at the Department of Clinical Biochemistry, Rigshospitalet, Glostrup Hospital, Denmark.

Participants

Healthy, sedentary postmenopausal women aged below 70 years were eligible to participate in the present study. Inclusion criteria were: non-smoking and body mass index (BMI) < 30 kg/m². Exclusion criteria were: T-score < -3 SD in the lumbar spine or hip; Z-score > 1.5 SD; use of hormone therapy, medical treatment, or supplements that affect bone metabolism; previous or current medical condition affecting bone health; engagement in regular and systemic weight-bearing training or strength training during the preceding two years.

A flow diagram is shown below: Initially, twenty women were recruited to the training via an online advertisement and a local newspaper, but only 19 showed up for pre-testing. After a medical examination, one participant was excluded due to low BMD (T-score < -3 SD), and two were excluded due to high BMI (≥ 30 kg/m²). In addition, one woman refrained from participating in the training, and thus, 15 participants were recruited to MMT. During the study, two participants in MMT dropped out due to personal reasons and at the end of the study four participants were excluded in the analyses as their average attendance to the program was less than one hour per week. CON consisted of 13 age-matched sedentary postmenopausal women (12 from a previous study plus the woman who refrained from participating in the training), and therefore 9 MMT and 13 CON was finally included in the data analyses.

A Feasibility Study of Training in a Local Community Aimed Upon Health Promotion with Special Emphasis on Musculoskeletal Health Effects

CONSORT Flow Diagram

Participants' baseline characteristics, including maximum oxygen consumption (VO₂-max), are shown in Table 1.

Table 1. Baseline characteristics of the participants

	MMT (n=9)	CON (n=13)	p-value
Age (years)	62.4 ± 3.8	58.7 ± 4.7	0.061
Height (cm)	166.9 ± 6.4	166.9 ± 5.2	0.989
Weight (kg)	72.8 ± 5.6	64.2 ± 10	0.022*
BMI (kg/m ²)	26.3 ± 2.2	22.9 ± 2.9	0.009*
Body Fat Percentage (%)	39.4 ± 3.1	33.7 ± 8.5	0.070
Total Fat Mass (kg)	28.7 ± 2.7	22.2 ± 8.6	0.043*
Total Lean Body Mass (kg)	41.8 ± 4.3	39.8 ± 3.4	0.233
VAT-mass (g)	793 ± 351.2	511 ± 434.8	0.123

A Feasibility Study of Training in a Local Community Aimed Upon Health Promotion with Special Emphasis on Musculoskeletal Health Effects

VAT-volume (cm ³)	840.6 ± 372.2	541.7 ± 460.9	0.123
Total BMC (g)	2266.9 ± 206.5	2067.2 ± 300.2	0.100
BMD (g/cm ²)			
Whole-body	1.121 ± 0.073	1.046 ± 0.099	0.066
Lumbar spine	1.088 ± 0.137	1.014 ± 0.111	0.175
Right Femur neck	0.918 ± 0.092	0.834 ± 0.097	0.057
Left Femur neck	0.941 ± 0.088	0.823 ± 0.076	0.003*
Mean Femur neck	0.929 ± 0.089	0.829 ± 0.085	0.015*
Right Total Femur	0.947 ± 0.098	0.864 ± 0.091	0.056
Left Total Femur	0.949 ± 0.101	0.840 ± 0.091	0.016*
Mean Total Femur	0.948 ± 0.098	0.852 ± 0.090	0.028*
Right Trochanter	0.741 ± 0.087	0.683 ± 0.092	0.149
Left Trochanter	0.745 ± 0.091	0.661 ± 0.097	0.055
Mean Trochanter	0.743 ± 0.086	0.672 ± 0.093	0.084
Right Shaft	1.151 ± 0.126	1.046 ± 0.125	0.068
Left Shaft	1.149 ± 0.131	1.008 ± 0.121	0.017*
Mean Shaft	1.150 ± 0.126	1.027 ± 0.121	0.033*
BTM			
P1NP (μg/l)	52.8 ± 16.6	62.1 ± 21.3	0.298
OC (μg/l)	19 ± 6.5	28.9 ± 7.1	0.003*
CTX (ng/l)	331.2 ± 100.7	627.8 ± 253.8	0.001*
VO ₂ max (ml/min/kg)	28.2 ± 3.6	30.5 ± 4.7	0.204

Values are given as means ± SD. BMI = body mass index, BMD = bone mineral density, BTM = bone turnover marker. *Significant difference between groups (p<0.05). Unpaired T-test.

Every participant was fully informed before giving her written informed consent to the procedures and potential discomfort associated with the study. The study was conducted in accordance with the Declaration of Helsinki and approved by the local ethics committee of the Capital Region of Denmark, H-18044190.

Training program

The present feasibility study evaluated the osteogenic impact of a training concept already offered by the health promotion initiative in a local community.

According to the initiative, the training was offered as “evidence-based bone training” aimed upon enhancing musculoskeletal health. It was carried out twice a week, 60 minutes each session. The training concept included: 1) High- and odd-impact exercise including multi-directional games; 2) Progressive resistance training; 3) Balance and coordination training. The participants were engaged in intermittent gymnastics and small game sessions aimed at imposing osteogenic and diverse strain on the skeleton, mainly in the legs and arms. Thus, the training included various jumping exercises (e.g., counter-movement jump, from the floor to the bench, and from one bench to the floor), quick walking up and down on gymnastics

equipment, sprinting over short distances in different directions (in small games form). In addition, resistance exercises with power band and elastic bands, heavy exercise balls (medicine balls), and sandbags of 5-7 kg were applied. The training was performed intermittent and varied to ensure that the bones would not be desensitized, as it is seen in endurance training.

BMD and body composition

To test the BMD exclusion criteria at baseline as well as evaluate bone adaptation after 19wk of training, BMD (g/cm^2) of proximal femur (PF), lumbar spine (LS), and whole-body (WB) were assessed by Dual-energy X-ray Absorptiometry scanning (iDXA, Lunar Corporation, Madison, Wisconsin, USA) according to standard procedures. The regions of interest were determined by the encore software (encore software version 14.10.022, GE Medical Systems, Madison, United States). In addition, body composition was evaluated by the whole-body scan: body weight (BW, kg), BMI (kg/m^2), body fat percentage (%BF, %), total fat mass (FM, g), total lean body mass (LBM, g), visceral adipose tissue (VAT) mass (g) and volume (m^3), and total bone mineral content (BMC, g). The participants were asked to remove metal objects and empty their bladder prior to scanning.

Blood sampling & Biochemical analyses

The plasma concentration of BTM at BASE, after 3wk, and after 19wk of training were measured. After an overnight fast and without any vigorous activities in the previous 48 hours, participants showed up in the laboratory in the early morning. Blood samples were collected from the antecubital vein with a butterfly needle, then transferred to EDTA tubes and centrifuged immediately. The plasma fractions were put on dry ice. Eighteen ml of blood were taken from each participant per test day. Following each test, a sample was placed at -80°C for future P1NP, OC, and CTX analysis, which were assessed by the Chemiluminescence method using a fully automated immunoassay system (iSYS, Immunodiagnostic Systems Ltd., Bolton, England). The assay performance expressed as inter-run variation coefficients were 8% for P1NP, 9% for OC, and 10% for CTX.

Training status

To estimate the participants' general training status, a progressive test of maximal oxygen uptake ($\text{VO}_2\text{-max}$) ($\text{ml}/\text{kg}/\text{min}$) was performed on an electronic ergometer cycle (Monark 839E, Monark Exercise AB, Vansbro, Sweden) according to standard procedures. A breath-by-breath gas online analyzing system (Jaeger Oxycon Pro, VIASYS Healthcare, Höchberg, Germany) was connected to the participant, and a direct $\text{VO}_2\text{-max}$ measurement was conducted.

Dynamic balance

The “four square step test” (FSST) was performed to evaluate the dynamic balance [18] in MMT. The test requires a person to move systematically forward, sideward, backward, and sideward again over four narrow sticks circa 2.5 cm in diameter and 100 cm in length placed on the floor like a cross. The participants were requested to complete the sequence as fast as possible without touching the sticks. The participants started by facing the cross in the lower left quadrant, stepped forward over the stick into the next left quadrant, stepped sideward over the stick again into the upper right quadrant, and stepped backward over the stick into the lower right quadrant, then stepped sideward over the stick into the left quadrant where they started. Thus, they were moving in a clockwise direction. The floor in each square must be contacted by both feet, and the participants were asked to face forward for the whole sequence if possible. The participants were allowed to turn to step into the next square if needed. They started and finished in the same square, and the score were given in seconds (sec). The test was done twice, and the fastest time was used as the FSST score.

Functional muscle strength and power

The functional muscle strength and power were evaluated in MMT by a jump-and-reach test (vertical jump height) (Vertec Sports Imports, Hilliard, OH). First, the participants were taught how to perform a countermovement jump and how to displace the vanes that was placed above reaching height on a vertical stand. After thoroughly instruction and familiarization, the jump-and-reach test was performed. The maximum vertical jump height (cm) was determined by the difference between the participant standing reach height and the highest displaced vane. The greatest value out of three trials was taken as the result.

Statistical analysis

All of the statistical analyses were conducted using the Statistical Package for the Social Sciences (SPSS, version 26.0, IBM Corp., Armonk, NY, USA). The standard descriptive statistics and unpaired T-test were used to describe and test the baseline characteristics of the participants. Repeated measurements ANOVA and general linear model with post hoc tests were used to test the effect of training on BTM, BMD, dynamic balance, and the jump-and-reach test. A p-value < 0.05 was considered significant.

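### The 3-week bone-marker results use MMT women chosen on 19-week attendance, so inclusion depends mostly on sessions held after that blood sample

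*Combined protocol and SAP*

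**What the plan says.** The opening overview sets the attendance condition: "average attendance rate of MMT participants over the 19wk had to be > 1 hour weekly". It also schedules an early blood draw: "After three weeks (3wk) of training, resting blood samples were collected again". The section on blood sampling and biochemical analyses confirms three marker time points: "The plasma concentration of BTM at BASE, after 3wk, and after 19wk of training were measured".

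The Participants section describes how the rule was used once the study had ended: "four participants were excluded in the analyses as their average attendance to the program was less than one hour per week". It then gives one set for the data analyses, 9 MMT and 13 CON.

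The Statistical analysis section tests the markers by repeated-measures ANOVA and a general linear model with post hoc tests. It names no separate population for the 3-week time point. No section confines the attendance rule to 19-week outcomes.

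**The concern.** A 3-week sample can reflect only the training done by week 3. The set used to report it is instead defined by behaviour up to week 19, most of which had not happened when the blood was drawn. This can go wrong in two ways. A woman fully exposed by week 3 who later lapses is left out of the 3-week result. A woman who hardly trained before the sample but came often afterwards is counted as trained at 3 weeks.

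Membership of the MMT group at 3 weeks is therefore conditioned on events after the outcome, and in MMT only, because CON has no attendance rule. If the reasons for lapsing are related to how a woman's markers behave, the 3-week change in the retained women need not represent that in the women who had trained by then. Usable 3-week samples may also be discarded from a very small group.

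Calling the nine women a per-protocol set would not settle this, because the set would still rest on weeks 4 to 19.

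**Working it through.** **The plan's own count (Participants section).** Twenty recruited, less 1 who did not show up, 1 with low BMD, 2 with high BMI and 1 who refrained: 20 − 1 − 1 − 2 − 1 = 15, matching "15 participants were recruited to MMT". Then 15 − 2 drop-outs − 4 for attendance = 9 MMT, as stated. CON: 12 + 1 = 13, as stated. The attendance rule removed 4 of the 13 women who did not drop out (31%).

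**Sessions that decide inclusion.** The overview says "Training was offered twice weekly for one hour", and the Training program section agrees: "It was carried out twice a week, 60 minutes each session". I assume even scheduling with no breaks, and six sessions held before the 3-week sample.

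- Total: 19 × 2 = 38 sessions, or 38 hours.
- Before the 3-week sample: 3 × 2 = 6 (6/38 = 16%).
- After it: 16 × 2 = 32 (32/38 = 84%).

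**Threshold.** An average of one hour a week is 19 hours. The overview requires more than that, so at least 20 sessions. The Participants section excludes those below it, so 19 would be enough.

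| Weeks 1–3 | Later | Total | Hours/week | Overview wording | Participants wording |
|---|---|---|---|---|---|
| 6 of 6 | 12 of 32 | 18 | 18/19 = 0.95 | removed | removed |
| 6 of 6 | 13 of 32 | 19 | 1.00 | fails | not excluded |
| 6 of 6 | 14 of 32 | 20 | 20/19 = 1.05 | kept | kept |
| 0 of 6 | 19 of 32 | 19 | 1.00 | fails | not excluded |
| 0 of 6 | 20 of 32 | 20 | 1.05 | kept | kept |

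The first and last rows show the problem, and both hold under either wording. Only a total of exactly 19 hours is left unclear.

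**Most that could be gained in precision.** Suppose all four women excluded for attendance have baseline and 3-week samples, so that MMT goes from 9 to 13, and that SDs are equal.

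- MMT mean change: the SE is proportional to 1/√n. Ratio √(9/13) = 0.83, a reduction of 17%.
- MMT-CON difference with 13 CON: ratio √[(1/13 + 1/13)/(1/9 + 1/13)] = √(0.1538/0.1880) = 0.90, a reduction of about 10%.

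If none of the four gave a 3-week sample, the gain is zero. The two drop-outs would be eligible too if they gave that sample, for a ceiling of 15, but the documents do not say when they left.

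**The case against.** **The planned model.** A classical repeated-measures ANOVA on three time points uses the same women throughout, so a common set follows from the method. This stands, and it affects the cost: the remedy needs a separate small analysis or a different model. It does not justify the window, because needing the same women at each time is a data requirement and does not call for a 19-week attendance filter.

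**An adherence rule for weeks 1–3 also selects.** It would still choose MMT women on behaviour after baseline. This stands as well. It is why the main 3-week analysis should take every MMT woman with both samples, with an early-adherence set only as an addition.

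**No bias is shown.** A reader might infer that the 3-week marker response is distorted in a known direction, for instance because poor early responders later stopped coming. The documents do not support that. They give no 3-week values and no attendance pattern for any excluded woman, and the two attendance patterns that fail are illustrations of the rule, not reported cases.

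**The gain may be overstated.** A reader might also take the 17% as the expected improvement. It is a ceiling, and it concerns the MMT change alone. Twelve of the 13 CON women came from a previous study, and the documents do not clearly show that they have 3-week samples, so even the 10% for the group difference is conditional.

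**It is late.** The document reports completed exclusions and calls the work a feasibility study. A new 3-week set defined after the data have been seen is post hoc and must be labelled so. That limits the weight of the added analysis but does not make the present set suitable for the 3-week question.

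**Conclusion.** The mismatch is real and limited to one time point. As written, inclusion in the 3-week P1NP, OC and CTX results is decided by a 19-week average to which later sessions contribute 84%. The rule therefore neither ensures exposure by week 3 nor avoids selecting on what happened afterwards.

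This rests on two assumptions: that sessions ran evenly over the 19 weeks, and that the 3-week results use the same nine MMT women. The second is inferred from the single set the plan gives; nothing contradicts it, and if another set was used the plan should say so.

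The documents support no statement about the direction or size of bias. The 19-week outcomes are not touched by this point, since for them the attendance window and the outcome window agree. It should be corrected, but it does not undermine the study as a whole.

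**What to change.** 1. State that the 19-week attendance rule applies to 19-week outcomes only.
2. Add a separate baseline-to-3-week marker analysis in every MMT woman with both samples, whatever her later attendance. A change-score analysis, a baseline-adjusted linear model, or a mixed model that does not need complete 19-week data would each do.
3. Reconcile the two wordings of the threshold, so that an average of exactly one hour a week is classified.
4. If an adherent 3-week set is also reported, define it from weeks 1–3 only, using the reconciled threshold: at least 3 of 6 sessions under the Participants wording, at least 4 of 6 under the overview wording.
5. Report how many women excluded for attendance, and how many drop-outs, gave a 3-week sample. Label the new analyses post hoc if the data have already been seen.

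The cost is a few sentences in the analysis section and one small extra analysis of samples already taken. If item 4 is used, it also needs a recount of the attendance records that the 19-week average required. The downside is that the 3-week and 19-week marker results will rest on different MMT sets, which must be stated beside the results.

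### The plan never makes the MMT minus CON difference in change the test of training, so within-group change, the time effect and post hoc results can each stand in for it

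*Combined protocol and SAP*

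**What the plan says.** The overview at the start of the document sets out two comparisons, one after the other: "After 19wk of training, all assessments were repeated and compared with baseline, and MMT and CON were finally compared". It does not say which of them decides whether training worked.

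The Statistical analysis section holds the whole inferential plan: "Repeated measurements ANOVA and general linear model with post hoc tests were used to test the effect of training on BTM, BMD, dynamic balance", with the jump-and-reach test added to the same list. The threshold is "A p-value < 0.05 was considered significant". The section does not mention a group-by-time interaction or a difference in change. It names no primary contrast, no adjustment or gating of the post hoc tests, and no tests that are only descriptive.

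The Dynamic balance section says that the four square step test "was performed to evaluate the dynamic balance [18] in MMT", and the section on functional muscle strength and power likewise places the jump test in MMT. The overview, by contrast, describes these tests at a visit attended by all participants.

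On numbers, the Participants section says "therefore 9 MMT and 13 CON was finally included in the data analyses". The controls are described as "12 from a previous study plus the woman who refrained from participating in the training".

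**The concern.** A repeated-measures model with two groups yields several results: a time effect, a group effect, a group-by-time effect and a set of post hoc pairs. Only group-by-time asks whether trained women changed differently from controls. A time main effect, a significant change within MMT, or significance in MMT but not in CON can all arise when both groups change by the same amount and training does nothing. Ageing, season or assay drift could produce such a change. The assay section gives inter-run variation of 8% to 10% and does not say whether all visits were run together.

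Because the plan attaches the effect of training to the whole family of tests, any of these results could be reported under that name. The control group exists to prevent this.

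**Working it through.** **The plan's own figures.** The document gives no sample size calculation, power, effect size or SD of change, so there is no design figure to reproduce. The participant flow does add up: 20 − 1 − 1 − 2 − 1 = 15 recruited to MMT; 15 − 2 − 4 = 9 analysed; 12 + 1 = 13 controls.

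**Inputs.** n = 9 (MMT) and 13 (CON), from the Participants section; alpha 0.05, from Statistical analysis. Assumed: two-sided tests, normally distributed changes, equal variances, the same true change δ in both groups (in units of the SD of individual change), and no training effect.

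**Formulas for two visits (non-central t).**
- Within-MMT paired test: non-centrality δ√9 = 3δ, 8 df.
- Within-CON paired test: δ√13 = 3.606δ, 12 df.
- Time main effect, unweighted mean of the two group means: standard error ½√(1/9 + 1/13) = ½ × 0.4336 = 0.2168; non-centrality δ/0.2168 = 4.612δ, 20 df.
- Group-by-time, which equals the pooled t-test on change scores: (δ − δ)/0.4336 = 0, 20 df.
- Significant in MMT but not in CON: P(MMT) × [1 − P(CON)].

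| Shared change δ | Within MMT | Within CON | MMT only | Time effect | Group-by-time |
|---|---|---|---|---|---|
| 0 | 5% | 5% | 5% | 5% | 5% |
| 0.25 | 10% | 13% | 9% | 20% | 5% |
| 0.5 | 26% | 38% | 16% | 59% | 5% |
| 0.7 | 46% | 64% | 16% | 87% | 5% |

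Simulation agrees with these values. If the within-MMT test uses the pooled error term (20 df), 26% becomes 30% and 46% becomes 52%.

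**Bone turnover markers, three visits.** With no change at all, testing all three visit pairs in MMT at 0.05 without adjustment or gating gives at least one false positive in about 13% of simulated studies per marker. With Bonferroni adjustment the rate is 4.6%; if the pairs are read only after a significant omnibus F, about 4.9%. The plan does not say which applies.

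**When drift differs between groups.** If drift differs by Δ, the group-by-time test has non-centrality Δ/0.4336. At Δ = 0.5 this is 1.153, a false-positive rate of about 20%; at Δ = 0.7 it is 1.614, about 34%.

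**Balance and jump.** No arithmetic is needed. The Statistical analysis section lists them as outcomes on which the effect of training is tested, while their own sections describe them in MMT. On that description only a change from baseline can be tested, so a retest or learning effect cannot be separated from training.

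**The case against.** The best defence is that a group comparison is planned. The overview opens and closes with it, and *finally* may mark order rather than rank. The sentence can be read as computing change and then comparing groups, and a repeated-measures model can contain group-by-time. All of that stands. It shows that the right contrast is available, but not that it is the one the plan relies on. The inclusion of balance and jump in the same sentence shows that the plan's wording already admits within-MMT change as an effect of training.

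A reader might infer more than the document supports:
- **That the plan declares a time effect or a change within MMT sufficient for BMD or bone markers.** It does not. The wording leaves this open.
- **That the post hoc tests are unadjusted.** The plan is silent, so the 13% is conditional. Gating also matters: if the within-MMT test were read only after a significant group-by-time result, the rate at a shared change of 0.5 SD would be about 2.4%, not 26%.
- **That post hoc tests for BMD can show only within-group change.** They can also compare MMT with CON at each visit.
- **That a benefit seen as stability in MMT and loss in CON would be missed.** The planned MMT–CON comparison could detect it if made on change: at a difference of 1.3 SD the power is 81%.
- **That naming the contrast cures drift in general.** Twelve of 13 controls come from a previous study, so season and assay-run effects need not be shared. Table 1 also shows large baseline differences (CTX 331.2 against 627.8 ng/l), so regression to the mean need not act equally in the two groups.

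**Conclusion.** The concern holds as an unspecified deciding test for BMD and bone markers, and as a missing comparator for balance and jump. If groups share a change of 0.25 to 0.7 SD and training has no effect, a within-MMT test is falsely positive in about 10% to 46% of studies and the time effect in about 20% to 87%, against 5% for the difference in change. These sizes rest on assumed drift, normal changes, equal variances and ungated reading of the tests. The direction does not depend on the drift chosen: any non-zero shared change raises the first two rates and leaves the third at 5%. The benefit of the correction is limited to drift that the two groups have in common.

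**What to change.** In Statistical analysis, add:

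> The effect of training on BTM and BMD is the MMT minus CON difference in change from BASE (group-by-time contrast): BASE to 19wk for BMD; BASE to 3wk and BASE to 19wk for BTM, adjusted for the two comparisons. Within-group changes and the time main effect are descriptive, given with 95% CIs, and are not evidence of a training effect. Balance and jump, where only MMT was tested, are reported as uncontrolled changes from baseline.

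In the overview, say that change from baseline was compared between MMT and CON, and reconcile whether CON did the balance and jump tests. State as a limitation that 12 of 13 controls come from a previous study, so the contrast removes only drift common to both groups.

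The cost is a few sentences and no new data. The downside is that a significant change seen only within MMT can no longer be claimed as a training effect. The remaining test is also not powerful with 9 against 13: about 42% for a true difference of 0.8 SD of change, 59% for 1.0 and 81% for 1.3.

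### The only stated analysis set is 9 of the 15 women who entered MMT, selected on attendance during training, with no per-protocol label and no all-entered analysis beside it

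*Combined protocol and SAP*

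**What the plan says.** The opening overview makes attendance a condition of the design: "the average attendance rate of MMT participants over the 19wk had to be > 1 hour weekly". The Participants section gives the flow. Fifteen women entered MMT, two left for personal reasons, and then "four participants were excluded in the analyses as their average attendance to the program was less than one hour per week". The outcome is that "9 MMT and 13 CON was finally included in the data analyses". The 13 controls are 12 women from a previous study plus one woman who was recruited for the training but chose not to take part.

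Table 1 shows MMT for n=9 only. The Statistical analysis section names repeated-measures ANOVA and a general linear model. It defines no analysis population, does not call the nine-woman set per-protocol, gives no missing-data method and describes no analysis of all entrants.

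The stated purpose points two ways. The overview says the training "was offered to postmenopausal healthy women in a local community" and the title is "A Feasibility Study of Training in a Local Community Aimed Upon Health Promotion", which suggest interest in the programme as a community offer. The Training program section says "The present feasibility study evaluated the osteogenic impact of a training concept already offered by the health promotion initiative", which can equally mean the effect in women who trained.

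**The concern.** Average attendance over 19 weeks is a post-baseline variable. Selecting on it in one group only means the nine women are compared with controls who passed no equivalent filter. If women who keep attending would have changed differently anyway (through health, motivation or other activity), part of the observed change reflects who stayed rather than what training did. This also affects dynamic balance and jump height, where there is no control comparison: "The functional muscle strength and power were evaluated in MMT by a jump-and-reach test", and the balance test is likewise described for MMT.

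The second risk is interpretation. In a feasibility study of a community programme, the women who entered and attended too little are part of the answer. With no label and no companion analysis, a reader may take the nine-woman result as the effect of the programme as offered.

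**Working it through.** **Inputs (Participants section).** 20 recruited; 1 did not appear for pre-testing; 1 excluded for low BMD; 2 for high BMI; 1 refrained from training; 2 dropped out; 4 removed for attendance; CON 12 + 1.

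**Reproducing the flow.** 20 − 1 − 1 − 2 = 16; 16 − 1 = 15 entered MMT; 15 − 2 − 4 = 9 analysed; 12 + 1 = 13 CON. All stated counts agree.

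**Share absent.** By the attendance rule: 4/13 = 31% of non-dropouts. With the dropouts: 6/15 = 40% of entrants.

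**Feasibility proportions (Clopper–Pearson 95% CI).**
- Met the attendance rule, of entrants: 9/15 = 60% (32–84%)
- Retained, of entrants: 13/15 = 87% (60–98%)
- Met the rule, with the woman who refrained also counted: 9/16 = 56% (30–80%)

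**Possible bias (illustration only).** No document gives a correlation r between attendance and non-training change, so r is assumed. Simulation: no training effect, standard normal change, top 9 on attendance kept.

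| r | Bias, 9 of 13 kept (SD) | Two-sided 5% error, within-MMT change | Bias, 9 of 15 kept (SD) |
|---|---|---|---|
| 0 | 0.00 | 5.0% | 0.00 |
| 0.1 | 0.05 | 5.2% | 0.06 |
| 0.3 | 0.14 | 7.0% | 0.18 |
| 0.5 | 0.24 | 11.1% | 0.31 |

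The last column assumes the two dropouts were also the lowest attenders. A negative r reverses the sign. For scale, the standard error of a 9 v 13 difference with equal SDs is √(1/9 + 1/13) = 0.434 SD.

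The same simulation gives error v CON of 5.1 / 6.2 / 8.6% for r = 0.1 / 0.3 / 0.5 (9 of 13 kept), but only if the groups are otherwise exchangeable. Table 1 contradicts that: OC (19 − 28.9)/6.87 = −1.44 and CTX (331.2 − 627.8)/206.7 = −1.44 pooled SD. Those rates therefore do not describe this trial.

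**What an all-entered analysis could add.** Let k be the number of the four low attenders with 19-week data, taking the dropouts as having none. With an assumed gap of 0.5 SD between the nine and the low attenders, the MMT mean shifts by 0.5 × k/(9 + k). The standard error v CON is √(1/(9 + k) + 1/13).

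| k | Low attenders' share | Shift (SD) | SE v CON (SD) | SE reduction |
|---|---|---|---|---|
| 0 | 0% | 0 | 0.434 | 0% |
| 1 | 10% | 0.05 | 0.421 | 3.0% |
| 2 | 18% | 0.09 | 0.410 | 5.5% |
| 3 | 25% | 0.13 | 0.400 | 7.7% |
| 4 | 31% | 0.15 | 0.392 | 9.5% |

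**The cut-off.** The overview requires more than one hour; the Participants section removes those below one hour. The two differ only at an average of exactly one hour. The four are described as below it, so they fail under both.

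**The case against.** The strongest reply is that nothing is hidden. The attendance condition is in the overview, every loss is counted and explained, and Table 1 is headed n=9. The Statistical analysis section speaks of the effect of training, which favours the effect in women who trained, and for that question the nine-woman set is a legitimate choice. This stands, and it is why that analysis should be kept. It does not supply the label or the companion analysis. The document is also dated December 2021 and reports recruitment in the past tense, so it cannot show when the rule was fixed.

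It is also fair to say that the fix may yield little. No section confirms 19-week data for any of the six. The sentence "all participants showed up in the laboratory at three occasions prior to the intervention" cannot be relied on for complete baseline data, because that account includes balance and jump tests that the test sections describe for MMT only. The 3-week sample is tied to three weeks of training, so CON may not have one. These limits stand and shape the fix.

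Three stronger readings are tempting and unsupported:
- **The reported effect is inflated, or the false-positive rate is raised by a known amount.** No correlation is given, the sign is unknown, and the error rates v CON need an exchangeability that Table 1 contradicts.
- **Analysing all 15 gives the effect of the programme as offered, like intention-to-treat.** It does not: the woman who refrained from training sits in CON, and there was no randomisation to preserve.
- **The inconsistent cut-off changed who was excluded.** On the text, it did not.

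**Conclusion.** The concern holds in a limited form, and the plan should be amended. As written, it yields only a minimum-attender estimate from 60% of the women who entered MMT, selected after baseline and in one group. The counts are certain. Bias is possible, but its size and direction cannot be learned from the documents; the 0.05 to 0.24 SD range rests wholly on assumed correlations of 0.1 to 0.5. The nine-woman analysis is acceptable if named for what it is, but not as the effect of the offered programme. An added analysis would reduce selection on attendance only. Confounding from a non-randomised, mostly external control group would be untouched.

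**What to change.** 1. Keep the nine-woman analysis and label it per-protocol (minimum attenders).
2. Beside it, report an analysis labelled post hoc of all 15 women who entered MMT, whatever their attendance, using all available data in a linear mixed model (SPSS MIXED). Compare with CON for BTM and BMD at visits where both groups were measured; report within-MMT change for balance and jump.
3. State, for each outcome, how many of the six have 19-week data, and that the model relies on data missing at random. If none has, say that no 19-week change could be added.
4. Call this analysis all who entered, not the programme as offered. Show the CON comparison also with the woman who refrained left out (12 controls).
5. Describe the nine and the six at baseline, where data exist.
6. Report 9/15, 13/15 and 9/16 with the exact intervals above.
7. Reconcile the two wordings of the attendance cut-off.
8. Do not present the nine-woman result as the effect of the offered programme, and state that confounding from the control group remains.

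Cost: revised wording, a fuller Table 1 and several added outcome models (three BTM, a number of BMD sites, balance and jump) on data already collected. Low attenders may dilute the estimate: if the six had a share f of the effect in the nine, the all-15 mean would be (9 + 6f)/15 of it, that is 60% at f = 0 and 80% at f = 0.5. If the six have no follow-up data, the gain for 19-week outcomes is nil and only the labelling and feasibility reporting improve.
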